Individuals with Late Life Depression (LLD) often have cognitive problems, particularly problems with memory, attention, and problem solving, all of which contribute to antidepressant non-response. Our group and others have shown that decreased thinking speed is the central cause of functional problems in patients with LLD. Similarly, decreased walking speed is associated with depression and carries additional risk for falls, hospitalization, and death. Available evidence suggests that declining functionality in the brain's dopamine system contributes to age-related cognitive and motor slowing. The central hypothesis of this R61/R33 Phased Innovation Award is that by enhancing dopamine functioning in the brain and improving cognitive and motor slowing, administration of carbidopa/levodopa (L-DOPA) will improve depressive symptoms in older adults.

This IRB protocol pertains to the R61 Phase of this grant proposal, and a separate IRB will be submitted subsequently for the R33 Phase. In the R61 Phase 60 adults aged > 60 years with (1) a DSM 5 depressive disorder, (2) significant depressive symptoms, (3) decreased thinking speed, and (4) decreased walking speed will receive 3 weeks of treatment with L-DOPA up to 450mg. We will test whether L-DOPA increases brain dopamine release using neuroimaging and whether it speeds up thinking and walking speed. If L-DOPA treatment achieves these goals, we will proceed to compare the best-tolerated dose of L-DOPA to placebo in the R33 Phase.

Data collected in the proposed studies may help identify a new treatment for LLD, which could have large public health ramifications given the prevalence, frequent treatment resistance, and chronicity characteristic of LLD. This project also will elucidate the neurobiology of slowing at molecular, structural, and functional levels of analysis, increasing our understanding of the interplay between these aging-associated processes and the pathophysiologic changes underlying late life neuropsychiatric disorders. Exploring patient characteristics that predict response to L-DOPA may provide useful information to guide differential therapeutics and develop personalized medicine for LLD.

Background, Significance and Rationale

Background, Significance and Rationale LLD affects 3% of community-dwelling adults over 60 years old (1), and 15% of older adults have

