ramifications given the prevalence, frequent treatment resistance, and chronicity characteristic of LLD. Even apart from patients with LLD, cognitive and motor slowing exact a large public health burden in terms of impaired functioning and increased morbidity and mortality, and this burden will only grow as the population ages. It is critical to develop treatments capable of altering the negative health trajectories associated with slowing in order to help older adults maintain independent functioning and live longer with an increased quality of life. Finally, while PET and MRI may prove critical to understand the neurobiology of slowing and LLD, their invasiveness and expense limit their roles in informing treatment decisions in clinical practice settings. For this reason we are also assessing the influence of genetic moderators such as interleukin-6 (IL-6) and catechol-O-methyl-transferase (COMT) genotype on baseline dopamine functioning and response to L-DOPA. This may facilitate the identification of both high-risk individuals and those most likely to benefit from treatment interventions.

Specific Aims and Hypotheses

Specific Aims and Hypotheses

We hypothesize that treatment with levodopa (L-DOPA) will improve depressive symptoms in LLD by enhancing striatal dopamine release and improving cognitive/motor slowing. In the R61 Phase, 60 adults aged > 60 years with (1) a DSM 5 depressive disorder, (2) significant depressive symptoms (CES-D > 10), (3) decreased processing speed (1 SD below age-adjusted norms on the Digit Symbol Test) and decreased gait speed (average walking speed over 15' course < 1m/s) will be receive 3 weeks of treatment with L-DOPA up to 450mg. A 300mg test dose will be tested for engagement of molecular target by determining whether L-DOPA displaces [11C]-raclopride on positron emission tomography (PET). If L-DOPA increases dopamine release and improves slowing at our proposed thresholds, we will proceed to compare the dose of L-DOPA exhibiting optimal target engagement to placebo in a subsequent R33 Phase.

R61 Phase.

Aim 1: To determine whether L-DOPA administration increases dopamine release.

Hypothesis 1: 300mg L-DOPA will reduce [11C]-raclopride binding potential (BP) in the caudate and putamen.

Aim 2: To determine whether L-DOPA increases processing and gait speed in depressed older adults.

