Hypothesis 2: 150mg, 300mg, and 450mg L-DOPA will increase processing and gait speed, with greatest improvement occurring at the 450mg dosage level.

Exploratory aims: To obtain information on the dosing and tolerability of L-DOPA in our patient population as well as identify PET and MRI biomarkers associated with slowing.

Description of Subject Population

Sample #1

Specify subject population

adults aged >59 years with a depressive disorder, decreased processing speed, and decreased gait speed Number of completers required to accomplish study aims

48

Projected number of subjects who will be enrolled to obtain required number of completers

Age range of subject population 60 years or older

Gender, Racial and Ethnic Breakdown

On the basis of previous depression studies conducted in the Adult and Late Life Depression Research Clinic, it is anticipated that the sample will be composed of 60% women and 40% men as well as approximately 75% Caucasian, 15% African American, and 10% Hispanic subjects.

On the basis of previous depression studies conducted in the Adult and Late Life Depression Research Clinic, it is anticipated that the sample will be composed of 60% women and 40% men. Description of subject population

This phase will enroll 60 outpatients who (1) are aged \geq 60 years, (2) diagnosed with Diagnostic and Statistical Manual (DSM) 5 (107) MDD, Dysthymia, or Depression Not Otherwise Specified (NOS), (3) have Center for Epidemiologic Studies-Depression Rating scale (CES-D) (108) score \geq 10, (4) have decreased gait speed (defined as average walking speed over 15' course \leq 1m/s), and (5) are willing to and capable of providing informed consent and complying with study procedures.

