- 13. Post-treatment scan: As close to the end of the 3 week study as possible (based on PET scheduling), subjects will undergo their post treatment scan. We will follow standard procedures for measuring L-DOPA-induced changes in synaptic dopamine levels set forth in PET studies of PD patients. Subjects will be given 75mg carbidopa/300mg L-DOPA approximately 1.5 hours before scanning. Subjects in week 3 of the protocol are taking 450mg LDOPA per day (150mg three times daily), so the 300mg administered prior to the post-treatment PET scan will constitute 300mg of their usual 450mg daily dose on the scan day. A low dose CT transmission scan is obtained prior to intravenous administration of 14mCi [11C] raclopride (or less). The start of tracer injection will be timed to coincide with the time of onset of L-DOPA effects (approximately 60-90 minutes following oral dose). Thus, the 60 minute PET scanning session will occur from 90 minutes to 150 minutes following L-DOPA dosing in all subjects. At the completion of the scan the IV catheter will be removed, and the subject will be evaluated (including mental status and vital signs) by a study physician. Vital signs, and physical exam will be performed prior to discharge from the PET suite.
- 14. We are aware that the scanning dose of 300mg given at once approximates but may not match the CNS effects of subchronic dosing with 150mg tid. However, this method has the advantages of being consistent with imaging studies of PD patients in which L-DOPA doses are typically 250-300mg and avoiding confounding of Δ BPND estimates by downregulation of D2 receptors occurring with subchronic administration. Since nausea is a known side effect of L-DOPA, we will be particularly vigilant about monitoring for it. When nausea occurs patients generally feel warm and sick to their stomachs. It will likely

occur after PET scanning, but if vomiting were necessary, the MD would remove the subject from the scanner so that vomiting does not occur while supine. Removal from the scanner can occur immediately.

- 15. PET data will be reconstructed into images using the appropriate reconstruction protocols and filters. PET images will be coregistered to the MRI and regional time activity curves will be measured. Data will be fitted to pharmacokinetic models, and relevant pharmacokinetic parameters, including the percent of receptors engaged by dopamine, will be estimated based on the model fitting procedures.

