- 16. Drs. [name] and [name] continue to be Co-Investigators responsible for neuroimaging as part of a subcontract executed between RFMH and SUNY-Stony Brook. They will lead analyses of neuroimaging data. In terms of on-site execution of PET and MRI scans, these are supervised by the study PI ([name]) and/or [name], who works with the Aging Program as a study clinician and has a research background in PET neuroimaging.

Clinical treatment

- 16. An effort will be made for all subjects to be titrated up to 450mg L-DOPA over a 3 week-duration study. We chose 450mg as the target dose because it is higher than doses known to affect cognition (i.e., 150-300mg) but lower than levels used for PD (i.e., 600-1200mg) that may have greater side effects. Each subject will start taking 37.5mg carbidopa/150 mg levodopa (1.5 25/100 sinemet tablets) once daily for one week, then increase to 75mg carbidopa/300mg levodopa (1.5 25/100 sinemet tablets twice daily) for one week, and finally increase to 112.5mg carbidopa/450mg levodopa (1.5 25/100 sinemet tablets three times daily) for one week. Each subject will be titrated to 450mg L-DOPA unless they cannot tolerate higher doses, in which case subjects will have their dosage reduced to the maximum tolerable dose.
- 17. Although each subject is titrated up to 450mg L-DOPA if it is tolerated, the study design allows us to assess the effects and tolerability of three different L-DOPA doses (150mg, 300mg, and 450mg). Based on published work using L-DOPA for PD, we expect effects on cognition and gait to be apparent at each dosing level approximately 5 days after dosage increases. By performing assessments weekly, we will thus obtain measures of L-DOPA's effect on processing and gait speed at each dosing level. We carefully reviewed the literature and consulted our Co-Investigator [name] (neurologist and PD expert) for evidence of carry-over effects of L-DOPA dosing (such that prior experience with 150mg and 300mg may influence a subject's experience of receiving 450mg). We found little evidence to suggest there are significant carry-over effects from previous L-DOPA doses, so each dose will be able to be assessed on its own merits. Similarly, we do not anticipate that the repeated assessments of processing and gait speeds will bias the study results.

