- 21. The following measures will be collected weekly throughout the study: 24-item HRSD, CGI Severity and Improvement, Structured Pill Count Interview, Unified Parkinson's Disease Rating Scale (UPDRS) (questions 32 and 33 will be used in this study to assess the duration and disability of dyskinesias caused by L-DOPA), Treatment Emergent Side Effect Scale, and Inventory of Depressive Symptoms—Self Report (IDS-SR).
- 22. In addition, processing and gait speed assessments will be performed weekly at 1pm to control for time of day effects and the duration since the last morning L-DOPA dose (anticipated to be 4 hours). Processing speed will be assessed using the Digit Symbol test from the Wechsler Adult Intelligence Scale-III (WAIS-III) (119) and the Pattern and Letter Comparison tests (120). These tests are all reliable and valid, with moderate to high loadings on the latent speed factor. A latent factor (and subsequent factor score) will be extracted from the 3-test battery pre- and post-treatment and used as the main outcome in the R61. By extracting a latent factor and factor loadings we will utilize a more pure measure of processing speed than if we used the raw scores from an individual test or a sum total score from the three raw scores combined (121-124).
- 23. Gait will be assessed as both a single and dual task (ST, DT) on a 15' walking course in the LLDC. For the ST, patients are instructed to walk at their usual or normal speed over the 15' walking course. For the DT, patients are instructed to walk at their usual pace while simultaneously verbally listing as many animals as possible (fluency DT). In addition, a counting DT will be used in which patients are instructed to walk at their usual pace while simultaneously performing serial subtractions by threes starting at 100 (125). Patients will start and end at a point 2 meters from beginning of the 15' course to eliminate acceleration and deceleration effects. Each ST and DT will be assessed two times with the average used in the analyses. The ST assessment of walking speed in m/s will be used as the primary outcome measure for this study.

End of study procedures

24. Following the 3 week duration treatment study, endpoint assessments will be made. Patients will enter 3 month open treatment period provided free of charge as described below.

You can upload charts or diagrams if any

Criteria for Early Discontinuation

Criteria for Early Discontinuation

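### In R61 each dose is tied to one week, so the weekly results cannot show that 450 mg works better than 150 mg, and no dose should go to R33 on that ordering alone

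*Combined protocol and SAP*

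**What the plan says.** Hypothesis 2 (Specific Aims and Hypotheses) predicts an ordering: "150mg, 300mg, and 450mg L-DOPA will increase processing and gait speed, with greatest improvement occurring at the 450mg dosage level".

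Clinical treatment, item 16, gives every subject 150 mg daily for one week, 300 mg for the next and 450 mg for the third. The only departure allowed is for subjects who cannot tolerate a higher dose, "in which case subjects will have their dosage reduced to the maximum tolerable dose". Under Assessments, item 22, "processing and gait speed assessments will be performed weekly at 1pm".

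Item 17 of Clinical treatment argues that the doses can be separated. It reports little evidence of carry-over from earlier doses and concludes: "so each dose will be able to be assessed on its own merits". On retesting it adds: "we do not anticipate that the repeated assessments of processing and gait speeds will bias the study results". No data are given for that expectation.

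The Statistical Analysis plan names chi-square and independent-samples t-tests for dose-dependent gains in speed. It has no term for time. The Summary of Experiences to Date already describes the gains in processing and gait speed as dose dependent.

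On the dose for the next phase, the Lay Summary says "we will proceed to compare the best-tolerated dose of L-DOPA to placebo in the R33 Phase", while Specific Aims says "we will proceed to compare the dose of L-DOPA exhibiting optimal target engagement to placebo in a subsequent R33 Phase". The only PET scan on drug follows a single 300 mg intake (PET Scanning, item 13).

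**The concern.** A one-way titration with repeated testing measures dose and visit number together. Little drug carry-over answers one question only: whether last week's dose still acts this week. It does not address learning of timed tests, expectancy in an open study, or improvement that simply takes three weeks of treatment to appear. Any such gain that continues from visit to visit puts 450 mg on top, which is the ordering Hypothesis 2 predicts.

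At stake are the reading of the reported dose dependence and, if target engagement in R33 is taken to mean the largest improvement in speed, the dose carried forward. Analysis is still ongoing and R33 is to have its own protocol, so both can still be handled correctly.

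**Working it through.** The documents give no power calculation or figure for comparing doses, so there is none to reproduce. Three checks follow.

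**1. Can dose and week be separated as planned?** Weeks 0, 1, 2, 3 carry 0, 150, 300, 450 mg, so dose = 150 × week and the correlation is 1.0. An intercept, three week indicators and three dose indicators make 7 columns of rank 4. With linear terms there are 3 columns of rank 2. No dose effect can be estimated free of a week effect.

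**2. Do dose reductions help?** Suppose some of the 48 planned completers drop from 450 to 300 mg in week 3 (the counts are assumed). With subject-centred linear week and dose terms, the variance inflation of the dose slope is 1/(1 − r²), where r is the correlation of dose with week. It is about 161, 65 and 33 for 2, 5 and 10 such subjects. The little information gained comes only from subjects selected by intolerance.

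**3. What could repeated testing do alone?** Inputs from the Summary of Experiences to Date: 36 participants and 8.3% drop-out, so 36 × (1 − 0.083) = 33.0 completers. Assumed, because the documents give neither: retest correlation ρ of 0.7 to 0.9, and gains g₁, g₂, g₃ (in baseline SD) at the week 1, 2 and 3 tests.

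The model is score = subject effect (variance ρ) + cumulative gain + error (variance 1 − ρ), with no drug effect. The step g₁ is common to all three doses. The expected 450 minus 150 mg difference is g₂ + g₃, with standard error √(2(1 − ρ)/33), which is 0.135, 0.110 and 0.078 for ρ = 0.7, 0.8 and 0.9.

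Results from 20,000 simulated trials per cell, for ρ = 0.7 / 0.8 / 0.9. The test is paired, 450 against 150 mg, two-sided 0.05:

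| g₁, g₂, g₃ | g₂ + g₃ | 450 mg ranks first (%) | Test favours 450 mg (%) |
|---|---|---|---|
| 0, 0, 0 | 0 | 33 / 33 / 33 | about 2.5 |
| 0.05 each | 0.10 | 55 / 61 / 71 | 11 / 14 / 24 |
| 0.10 each | 0.20 | 74 / 81 / 90 | 30 / 42 / 70 |
| 0.10, 0.05, 0.025 | 0.075 | 48 / 51 / 57 | 8 / 10 / 15 |
| all at g₁ or earlier | 0 | 33 / 33 / 33 | about 2.5 |

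The fourth row reflects an exposure before any drug. Evaluation, items 3 and 4, already gives the processing-speed tests and single-task gait, and Assessments, item 19, lists that visit separately from weeks 0-3. If gains run 0.20, 0.10, 0.05, 0.025, the first falls between screening and week 0. Treating week 0 as the first exposure (0.20, 0.10, 0.05) would instead put 450 mg first in about 60-73%.

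With the planned 48 completers, the two constant-gain rows together span about 60-94% ranking first.

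**Precision of a within-subject comparison.** The 95% half-width at 33 completers is t(0.975, 32) × √(2(1 − ρ)/33) = 2.04 × 0.135, 0.110 or 0.078, so about ±0.27, ±0.22 or ±0.16 SD. Treating the two weeks as independent groups gives a standard error of √(2/33) = 0.246 SD, because the pairing is ignored.

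**The case against.** The strongest reply is that item 17 states its assumptions openly. Carry-over was checked against the literature and with a neurologist, and no retest bias is anticipated. If both assumptions hold and nothing else changes with time, each dose is assessable. It is therefore too strong to call the statement false. What stands is that the design neither supports nor can test it, and that the two assumptions omit expectancy and time on treatment.

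The screening tests also matter. Practice gains usually shrink, and the largest step may come before week 0. The fourth row of the table allows for this and lowers the figures without removing the confounding. The documents do not say outright which visit is the baseline, and dual-task gait is not listed at screening.

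The gains are assumed, and the simulation describes one generic outcome. Nothing here establishes a retest gain for gait speed, so the percentages should not be carried over to it.

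A reader might infer that PET was meant to rank the doses and cannot. The documents do not say so: Specific Aims uses PET to ask whether a 300 mg test dose displaces the tracer, and PET Scanning, item 14, concedes that "the scanning dose of 300mg given at once approximates but may not match the CNS effects of subchronic dosing with 150mg tid".

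A reader might also infer from the two dose criteria that R33 lacks a workable rule. One criterion sits in a lay summary, the thresholds and the grant application are not in these pages, and R33 has a later protocol. The mismatch is real but can be settled there.

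**Conclusion.** The concern holds as a limit on interpretation. Planned dose and week are fully confounded, and reductions for intolerance add almost nothing. Neither the Hypothesis 2 ordering nor the reported dose dependence shows that 450 mg is better than 150 mg.

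The size of the bias is unknown. With no drug effect, 33 completers and ρ of 0.7-0.9, 450 mg ranks first in about 55-90% of trials under constant gains of 0.05-0.10 SD, in about 48-57% under shrinking gains after the screening exposure, and in 33% if all gain comes before or at the first on-drug test. The confounding itself needs no assumption. Every percentage does.

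Two stronger readings are tempting and unsupported. One is that L-DOPA has no effect, or that 450 mg is no better than 150 mg: the data cannot show that either. The other is that R33 will carry the wrong dose: the weekly ordering drives that choice only if target engagement is read as the largest improvement in speed, which the documents do not say.

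**What to change.** 1. In the SAP and the report, state that comparisons between doses include any effect of time and repeated testing. Do not conclude a dose-response or a best dose from the weekly ordering alone. Interventions are complete, so leave the protocol text as the record of the plan.

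2. For dose comparisons, replace the independent-samples t-tests in the SAP with within-subject between-dose differences and 95% confidence intervals, by dose actually taken. Report how many subjects reached, reduced and stopped each dose. Show the results over a range of retest gains labelled as assumptions, for example 0 to 0.15 SD per visit, including shrinking patterns. The upper end is a stress value: 3 × 0.15 = 0.45, just above the reported 450 mg processing-speed effect of 0.41 if that is in baseline SD units, which the documents do not state. Use the change from screening to week 0 as a guide where both were measured.

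3. In the R33 protocol, state one dose criterion in place of the two. Do not base it only on the largest week-by-week improvement. Note that PET informs on 300 mg only, and disclose that the rule was set after the R61 results were seen.

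The cost is some rewording and one analysis paragraph, with no new data. The dose-response conclusion becomes weaker. With intervals of about ±0.16 to ±0.27 SD before the retest range is added, R61 may not be able to name one best dose.

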4. MMSE

5. Clinical interview, HRSD

(MMSE) < 25

5. HRSD \geq 25

or the

presence of significant

significant suicide risk

6. current or recent (within the past 4 weeks)

treatment with antidepressants, antipsychotics, dopaminergic agents, or mood stabilizers

7. history of allergy,

hypersensitivity

reaction, or severe

intolerance to

L-DOPA 8. acute,

severe, or unstable

medical or

7. Clinical interview

6. Clinical interview

8. Clinical interview, physical exam

Page 13 of 43

neurological

illness

9. mobility

limiting

osteoarthritis of

any lower

extremity

joints,

symptomatic

lumbar spine

disease,

mobility

limiting history

of joint

replacement

surgery, or

history of spine

surgery

9. Clinical interview, physical exam

FOR SUBJECTS RECEIVING PET SCANS

ONLY:

10. having contraindicatio

n to MRI

scanning (such

as metal in body) or unable

to tolerate the

scanning

procedures

11. history of

significant

radio activity

exposure

(nuclear

medicine

studies or

occupational

10. MRI safety screening form

11. Clinical interview

exposure)

Waiver of Consent/Authorization

Indicate if you are requesting any of the following consent waivers

Waiver of consent for use of records that include protected health information (a HIPAA waiver of Authorization)

No

Waiver or alteration of consent

No

Waiver of documentation of consent

No

Waiver of parental consent

No

Consent Procedures

Is eligibility screening for this study conducted under a different IRB protocol?

Yes

Indicate NYSPI IRB #

6395R

Describe Study Consent Procedures

Following the study screening procedures, a study clinician authorized to obtain patient consent will explain the study procedures along with the attendant risks, benefits, and alternatives, including the anticipated outcome of doing nothing. The study clinician will then leave the room while the potential subject reads the consent form and return to answer any questions the subject has. Subjects who wish to participate will sign the consent form, while those who do not wish to participate will receive appropriate referrals.

Indicate which of the following are employed as a part of screening or main study consent procedures

✓ Consent Form

Persons designated to discuss and document consent

Select the names of persons designated to obtain consent/assent

[name], MD

No

[name], MD

Type in the name(s) not found in the above list

Study Procedures

Describe the procedures required for this study

Evaluation

1. Every subject evaluated for this protocol will receive a clinical interview by a psychiatrist or psychologist, be administered the Center for Epidemiologic Studies Depression Scale (CES-D) and the 24-item Hamilton Rating Scale for Depression (HRSD), and have a SCID performed by a trained rater. If a subject has a diagnosis of Major Depressive Disorder (MDD) or Dysthymia, he/she will be informed of this and educated about the availability of treatments for depression. If a subject is not interested in depression treatment and/or prefers to begin with an experimental treatment for slowing and depression, he/she will be offered participation in the present study provided their HRSD \leq 25 and there is no suicidal ideation present. Severe MDD (i.e., HRSD \geq 25) and/or the presence of significant suicide risk (e.g., suicidal ideation, clinician judgement that there is significant risk of suicide) are exclusions for this study.

Patients with Depression NOS will be educated that as yet, there are no FDA-approved treatments for their condition. Based on the extant data supporting the efficacy of antidepressants for MDD and Dysthymia, they will be informed that antidepressant treatment would be a very reasonable option for their condition. These potential subjects will be offered the option of being referred out for depression treatment, and it will be clarified that L-DOPA is not as yet a treatment for MDD. Thus, all potential participants in this study must state their preference not to be treated with a standard treatment for depression.

- 2. Participants signing informed consent will have documentation of vital signs, medical history (including history of head injury, stroke, hypertension, cardiac disease, thyroid disease, other medical conditions, surgeries, hospitalizations, and current medications), physical exam, urine drug screen, CBC, chemistries and electrolytes, thyroid profile, vitamin B12 and folate levels, urine analysis, standing/supine systolic/diastolic BP, and ECG.
- 3. Next, processing speed will be assessed using Digit Symbol test from the WAIS-III, the Trail Making Test Part A, the Pattern Comparison Test, and the Letter Comparison Test. Previous research established that these tests were all reliable and valid (moderate to high loadings on the latent speed factor). Digit Symbol or Trails A will be used as a selection criterion, with patients included in this study if they scored 0.5 SD below the age-adjusted norms on Digit Symbol or Trails A. A latent factor (and subsequent factor score) will be extracted from the 3-test battery pre- and post-treatment and used as the main outcome in this pilot study. By extracting a latent factor and factor loadings we will utilize a more pure measure of processing speed for pre- post-testing than if we used the raw scores from an individual test or a sum total score from the three raw scores combined.
- 4. Patients' gait will be assessed as walking speed in m/s on a 15' walking course. Patients are instructed to walk at their usual or normal speed for a total of 27' (starting and ending at a point 6 feet prior to and after the 15' course to eliminate acceleration and deceleration effects). Two trials will be completed, and gait speed will be based on the average of 2 trials. Gait speed will be used as a selection criterion, with patients included in this study if they have a gait speed < 1 m/s.

5. Subjects will return the following week to review the results of the above testing. If subjects continue to be eligible for the study after review of their processing speed and gait speed, they will continue as below. Subjects who do not meet selection criteria after processing and gait speed measurement will be referred out.

MRI Scanning

- 6. Half of the total sample will undergo neuroimaging (N=30 of total N=60). Subjects will undergo a pretreatment MRI and PET scan and a post-treatment MRI and PET scan (i.e., 2 total MRIs, 2 total PET scans, separated by the 3 week clinical trial). Subjects who do not meet imaging selection criteria or who do not wish to undergo scanning will be allowed to participate in the clinical trial portion of the study only. MRI and PET scanning may occur on the same day if this can be scheduled (MRI occurring first, followed by PET scan). However, due to the tightness of scheduling for these scanners, it is more likely that the MRI and PET scans will occur on different days--one day for MRI scan and one day for the PET scan. Typically the MRI scanning day will come before the PET scanning day.
- 7. MRI of the brain will be acquired using a GE MR750 3.0T System. At the start of the session, a 3-Plane localizer (scout) will be acquired to determine patient position. Subjects will then receive T1-weighted 3D SPGR (Spoiled Gradient Echo), T2 FLAIR, and EPI scans. Acquisition parameters for the EPI scans will be: TE/TR (ms) 20/2000; Flip Angle (deg) 720; in-plane resolution (voxels) 112x112; slice thickness/gap (mm) 3/0; slices 41.
- 8. For the MRI procedures, participants are instructed to lie as still as possible within the magnet. The MRI scan is completed in one session, and lasts for a total of 60 minutes. All precautions and protections are given to the participant to ensure that they are as safe and as comfortable as possible. For participants' comfort within the scanner, they lie on a padded table with a pillow to rest their heads on. A blanket is also provided to keep participants warm during the procedure. If the participant appears nervous or anxious, a trained member of the research staff remains with them inside the scanning suite for the duration of the scan. The participant is given a squeeze ball to terminate the scan at any time. If he/she squeezes the ball, he/she will be removed from the scanner immediately. Participants may decline the MRI scans at any time. If the participant chooses not to be scanned, his/her participation in the study will not be affected. Of course, a structural MRI scan would be required to participate in the PET scans. Any subject who cannot have at least a structural MRI scan would not be able to participate in this protocol. All of the MRI procedures are conducted on the 3-Tesla MRI scanner at the New York State Psychiatric Institute. Conducting these procedures will be an accredited Magnetic Resonance Technologist and one member of the research staff (Bachelor's Level or Higher), or [name] or [name], present.

PET Scanning

9. The neuroimaging subset of depressed subjects will have 2 [11C]-raclopride PET scans: (1) pre-treatment and (2) post-treatment (at the end of the 3 week duration trial).

- 10. PET experiments will be conducted with the mCT scanner in the PET Suite on the R1 level of the Public Health Building. Subjects participating in the study will be escorted on PET scan day by a research staff member to the R1 level of the Public Health Building where the PET scanner is located. A research staff person will stay with the subject at all times throughout the procedure and during transportation to and from the PET Center. The preparation of the subject will include the placement of a venous catheter.
- 11. The radiochemistry laboratory and PET suite staff will be in frequent communication regarding the status of preparation of the research subject (such as placement of venous line) and the progress of the radiotracer synthesis. As scan time approaches, the subject will be placed in a supine position on the camera table and will have vital signs (blood pressure and heart rate) obtained. Head will be positioned and a headholder will be used to decrease head movement during the scan.
- 12. Baseline scan: A low dose CT transmission scan is then obtained prior [11C] raclopride administration. At the end of the transmission scan, a maximum of 14 mCi of [11C] raclopride will be injected intravenously. The dose of [11C] raclopride, diluted in a 10 cc syringe, will be given as a single bolus over a period of 30 seconds. [11C] raclopride will be prepared by the central radio-ligand staff of the PET Center and will be administered by an approved Nuclear Medicine physician (Drs. [name], [name], or [name]). Study physicians will be present for all radiotracer injections. All study physicians have New York State Medical license and have had extensive training and experience with these types of PET studies. [11C] raclopride will be synthesized and tested for purity and sterility according to our standard procedure. The injected dose of [11C]-raclopride for each scan will not exceed 14 mCi, and lower amounts will be permitted. The study physician or Nuclear Medicine physician will evaluate the reconstructed PET image in order to ensure tracer uptake in the brain and will inform the radiochemist if there is a lack of expected uptake in the brain. All subjects will be monitored by the study physician at the time of injection and a study physician or nurse will be present in the PET suite.
- 13. Post-treatment scan: As close to the end of the 3 week study as possible (based on PET scheduling), subjects will undergo their post treatment scan. We will follow standard procedures for measuring L-DOPA-induced changes in synaptic dopamine levels set forth in PET studies of PD patients. Subjects will be given 75mg carbidopa/300mg L-DOPA approximately 1.5 hours before scanning. Subjects in week 3 of the protocol are taking 450mg LDOPA per day (150mg three times daily), so the 300mg administered prior to the post-treatment PET scan will constitute 300mg of their usual 450mg daily dose on the scan day. A low dose CT transmission scan is obtained prior to intravenous administration of 14mCi [11C] raclopride (or less). The start of tracer injection will be timed to coincide with the time of onset of L-DOPA effects (approximately 60-90 minutes following oral dose). Thus, the 60 minute PET scanning session will occur from 90 minutes to 150 minutes following L-DOPA dosing in all subjects. At the completion of the scan the IV catheter will be removed, and the subject will be evaluated (including mental status and vital signs) by a study physician. Vital signs, and physical exam will be performed prior to discharge from the PET suite.
- 14. We are aware that the scanning dose of 300mg given at once approximates but may not match the CNS effects of subchronic dosing with 150mg tid. However, this method has the advantages of being consistent with imaging studies of PD patients in which L-DOPA doses are typically 250-300mg and avoiding confounding of Δ BPND estimates by downregulation of D2 receptors occurring with subchronic administration. Since nausea is a known side effect of L-DOPA, we will be particularly vigilant about monitoring for it. When nausea occurs patients generally feel warm and sick to their stomachs. It will likely

occur after PET scanning, but if vomiting were necessary, the MD would remove the subject from the scanner so that vomiting does not occur while supine. Removal from the scanner can occur immediately.

- 15. PET data will be reconstructed into images using the appropriate reconstruction protocols and filters. PET images will be coregistered to the MRI and regional time activity curves will be measured. Data will be fitted to pharmacokinetic models, and relevant pharmacokinetic parameters, including the percent of receptors engaged by dopamine, will be estimated based on the model fitting procedures.
- 16. Drs. [name] and [name] continue to be Co-Investigators responsible for neuroimaging as part of a subcontract executed between RFMH and SUNY-Stony Brook. They will lead analyses of neuroimaging data. In terms of on-site execution of PET and MRI scans, these are supervised by the study PI ([name]) and/or [name], who works with the Aging Program as a study clinician and has a research background in PET neuroimaging.

Clinical treatment

- 16. An effort will be made for all subjects to be titrated up to 450mg L-DOPA over a 3 week-duration study. We chose 450mg as the target dose because it is higher than doses known to affect cognition (i.e., 150-300mg) but lower than levels used for PD (i.e., 600-1200mg) that may have greater side effects. Each subject will start taking 37.5mg carbidopa/150 mg levodopa (1.5 25/100 sinemet tablets) once daily for one week, then increase to 75mg carbidopa/300mg levodopa (1.5 25/100 sinemet tablets twice daily) for one week, and finally increase to 112.5mg carbidopa/450mg levodopa (1.5 25/100 sinemet tablets three times daily) for one week. Each subject will be titrated to 450mg L-DOPA unless they cannot tolerate higher doses, in which case subjects will have their dosage reduced to the maximum tolerable dose.
- 17. Although each subject is titrated up to 450mg L-DOPA if it is tolerated, the study design allows us to assess the effects and tolerability of three different L-DOPA doses (150mg, 300mg, and 450mg). Based on published work using L-DOPA for PD, we expect effects on cognition and gait to be apparent at each dosing level approximately 5 days after dosage increases. By performing assessments weekly, we will thus obtain measures of L-DOPA's effect on processing and gait speed at each dosing level. We carefully reviewed the literature and consulted our Co-Investigator [name] (neurologist and PD expert) for evidence of carry-over effects of L-DOPA dosing (such that prior experience with 150mg and 300mg may influence a subject's experience of receiving 450mg). We found little evidence to suggest there are significant carry-over effects from previous L-DOPA doses, so each dose will be able to be assessed on its own merits. Similarly, we do not anticipate that the repeated assessments of processing and gait speeds will bias the study results.
